## **4. AIMS & HYPOTHESES**

### **4.1 Aims:**

- 1) To develop and determine the feasibility of a training program which targets movement of food / liquid in the mouth with the use of ultrasound visual feedback and principles of motor learning to rehabilitate oral phase swallowing disorders amongst PwPD.
- 2) To determine the effectiveness of the developed training program on improving the efficiency of swallowing and QOL in PwPD.

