#### Schedule for individual participants from recruitment to follow-up:

**Tasks and Data Collected during Assessment and Probes:**

TIMING	Screener	Assessment	Phase: A1 Baseline Pre-treatment Baseline Probes	Phase: B Treatment Probes	Phase: A2 Baseline post-treatment		Phase C: Four week follow up
					Post-treatment Assessment	Maintenance Probes	
TASKS		1-2 visits	three times weekly across baseline period	1st and 3rd therapy session each week,	same day as the 1st maintenance probe	three times weekly across the baseline period	once, 4 weeks after the last therapy session
Screening (Questionnaire of demographic Information and inclusion/exclusion criteria)	X						
Timed Water Swallow Test (Hughes & Wiles, 1996; Sarve et al., 2021) (Video Recording)		X	X	X	X	X	X
Test of Mastication and Swallowing Solids (Athukorala et al., 2014; Huckabee et al., 2018) (Video Recording)		X	X	X	X	X	X
Information regarding time taken to complete meal and IDDSI Level (Cichero et al., 2017) (Images of food, Questionnaire)		X	X	X	X	X	X
Clinical Swallow Evaluation with Ultrasound using the MBSImp Rating Scale (Martin-Harris et al., 2008) for oral phase components (Video recording)		X	X	X	X	X	X

Swallowing Quality of Life Questionnaire (SWAL-QoL) (Questionnaire) (McHorney et al., 2002)		X				X		X
Theoretical Framework of Acceptability Questionnaire (Sekhon, Cartwright & Francis, 2022) (Questionnaire)						X		
Maximum Phonation Time (MPT) (Speyer et al., 2010) (Audio Recording)		X	X	X	X	X	X	X
Swallowing Disturbance Questionnaire (SDQ-PD) (Manor et al., 2007) (Questionnaire)	X					X		X
30 second monologue (Audio Recording)		X	X	X	X	X	X	X
North Wind and the Sun passage (Amundsen & Hansen, 2014) (Audio Recording)		X				X		X
Picture description (Audio Recording)		X				X		X
Rate at which participants can accurately repeat a series of rapid, alternating sounds as per published normative data (Kent, Kim & Chen, 2022) (Video Recording)		X	X	X	X	X	X	X

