## Probes

As shown on page 8, Probes for Phase A1 and A2: The TWST and TOMASS and a measurement of maximum phonation time and a 30 second monologue will be obtained 6 times for those allocated in the 2-week baseline periods and 9 times for those allocated in the 3-week baseline period.

Probes for Phase B: Treatment probes will be taken twice weekly (on the day of the first and last therapy session each week) for 4 weeks. Treatment probes will be identical to the baseline probes and will be collected immediately before therapy commences on that day.

The probes will take approximately 30-40 minutes and breaks will be provided if a participant experiences fatigue.

After the end of Phase B, a repeat assessment will be completed (identical to the one conducted at the start of the treatment program) by a qualified speech pathologist. Participants will also be asked to complete a Theoretical Framework of Acceptability Questionnaire to understand their acceptance and the feasibility of the intervention.

As this is a pilot, the frequency and duration of the treatment sessions, the duration and frequency of breaks provided, the type of foods and fluids used, the amount and type of feedback provided and the number of times the participant is asked to swallow and sets of swallows may be altered based on participants' fatigue level and response to the therapy protocol.

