## 6.7 Participant Withdrawal

Participants will be advised that they are free to withdraw from the study at any time including before, during or after the treatment has ceased. They may notify any of the research team members of their withdrawal. They may withdraw without any consequences or negative impact on their relationship with the University, the University SPEECH Clinic, the researchers, or the profession (Speech Pathology). The participant's individual data will stop being collected at the point of their withdrawal and their withdrawal will be recorded in the data management system (RedCap) within one business day of their withdrawal.

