### 6.7.1 Reasons for withdrawal

If the participants withdraw from the study prior to the conclusion, they will be asked for their reasons for withdrawal and if they consent to us retaining data that has already been

collected. If the participants consent to their data being retained, the data will be analysed using Intention to Treat Analysis.

The researchers may also withdraw participants from the study if they are non-compliant with the treatment protocol (e.g., cannot commit to the sessions) or are no longer eligible for the study due to changes in medical status (e.g., onset of stroke). If this occurs then the USYD HREC will be advised.

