## 9. CONSUMER REFERENCE GROUP

Participants within the study will serve as a consumer reference group within the pilot by providing feedback on the intervention based on the theoretical framework of acceptability (TFA). Their involvement as a consumer reference group is included in the participant information statement.

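### The acceptability questionnaire is given once, after Phase B, so participants who withdraw or are withdrawn before then give no acceptability rating

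*Protocol*

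**What the plan says.** Section 4.1 gives the first aim as "To develop and determine the feasibility of a training program". The measure linked to that aim is in the Probes text of section 6.2: "Participants will also be asked to complete a Theoretical Framework of Acceptability Questionnaire to understand their acceptance and the feasibility of the intervention". Section 6.5 lists the same questionnaire among the secondary, patient-reported outcomes. Section 9 gives it a second use: "Participants within the study will serve as a consumer reference group within the pilot by providing feedback on the intervention", with that feedback structured by the same framework.

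The timing is consistent within the protocol. The Probes text places the questionnaire with the post-treatment visit ("After the end of Phase B, a repeat assessment will be completed"). In the unnumbered schedule table of section 6.2, the row for the "Theoretical Framework of Acceptability Questionnaire" has a single mark, in the post-treatment block. The SWAL-QoL row has three marks.

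On leaving the study, section 6.7 states: "The participant's individual data will stop being collected at the point of their withdrawal". Under section 6.7.1, participants who withdraw themselves are treated as follows: "they will be asked for their reasons for withdrawal". The same section adds: "The researchers may also withdraw participants from the study if they are non-compliant with the treatment protocol". For that second group the only step described is to advise the ethics committee.

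**The concern.** Whether a rating exists depends on something close to what is being rated. Treatment visits last 45 to 60 minutes with up to 50 swallows, and on probe days 30 to 40 minutes of probes come before therapy. Section 8.1 anticipates fatigue from the intensity of therapy, and fullness or nausea. Section 6.3 expects attrition. Someone who leaves for one of these reasons has the most to say about acceptability, yet leaves before the questionnaire is due.

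The intention-to-treat handling in sections 6.7.1 and 6.7.2 does not help. The timed water swallow test and TOMASS have repeated values before a withdrawal, but the acceptability questionnaire has none. An analysis plan cannot recover a rating that was never taken, so this has to be settled in the protocol's schedule. At stake are the reading of Aim 1 and the feedback from the consumer reference group, both of which could rest on a selected set of raters.

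**Working it through.** The protocol gives no acceptability threshold, expected score or dropout rate, so there is no figure of its own to reproduce. The check sets the rules side by side and then counts ratings.

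**Step 1: the rules**

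| Situation | What the protocol provides | Acceptability rating? |
|---|---|---|
| Completes Phase B and attends the post-treatment assessment | Questionnaire at that visit (6.2, schedule table and Probes) | Yes |
| Withdraws by own choice before that visit | Data collection stops (6.7); reasons asked (6.7.1) | No |
| Withdrawn by the researchers before that visit | Data collection stops (6.7); ethics committee advised (6.7.1) | No |
| Stops sessions but stays enrolled | Not addressed | Possible |

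The loss is certain for the second and third rows only.

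**Step 2: how many ratings could be lost**

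The planned number is n = 6, with a minimum of 3 (Synopsis; 6.3; 6.7.3). With k leavers, the share without a rating is k/6:

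- k = 1: 1/6 = 17%
- k = 2: 2/6 = 33%
- k = 3: 3/6 = 50%

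**Step 3: how likely any loss is**

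Let d be the probability that a participant leaves before the post-treatment assessment, assumed independent between participants. The protocol does not state d, so a range is shown. The chance of at least one missing rating is 1 − (1 − d)^6, and the expected number of raters is 6(1 − d).

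| Assumed d | Chance of at least one missing rating | Expected raters of 6 |
|---|---|---|
| 10% | 1 − 0.9^6 = 47% | 5.4 |
| 20% | 1 − 0.8^6 = 74% | 4.8 |
| 30% | 1 − 0.7^6 = 88% | 4.2 |
| 50% | 1 − 0.5^6 = 98% | 3.0 |

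The 50% row is an outer case. It corresponds to falling from six to the minimum of three, but three is a design minimum and not a forecast of attrition.

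**Step 4: direction**

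If people leave because of burden, the missing ratings would probably be lower than those obtained, and the result is flattering. If they leave for an unrelated reason, such as the stroke example in section 6.7.1, there is no clear direction. The protocol gives no basis for a size on the questionnaire's own scale, so none is offered.

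**The case against.** The strongest reply is that nothing here contradicts itself. Rating an intervention once it is over is a coherent choice for a secondary outcome, and the table and text agree on it. The Probes text also allows the frequency, length and content of sessions to be altered for fatigue or response, so burden need not end in withdrawal. That is fair, and it lowers the likely number of leavers. It does not provide a rating from those who still leave.

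A reader might go further than the documents allow in three ways.

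- **That Aim 1 is answered only by those who tolerated the programme.** This is too strong. Part 1 assesses feasibility in a single participant. Withdrawals are recorded within one business day, reasons are asked of those who choose to leave, and adverse events are recorded. These are real information on leavers. What remains is that the protocol does not say they feed Aim 1, and a stated reason for leaving is not a rating on the framework.
- **That anyone who stops therapy early is lost.** The protocol does not equate stopping sessions with leaving the study. A participant who stops but stays enrolled could still be asked.
- **That replacements would hide the loss behind a full sample of six.** Section 6.7.3 seeks replacements only to secure a minimum of three. With up to three of six leaving, that minimum is still met and no replacement is required.

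It can also be said that an exit questionnaire conflicts with section 6.7 and that no exit contact exists for researcher-initiated withdrawals. Both are correct, and the fix has to deal with them.

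**Conclusion.** The point holds in a limited form. The only listed measure that the protocol links to acceptance and feasibility is missing by design for anyone who withdraws or is withdrawn before the post-treatment assessment. The acceptability result will therefore describe those who stayed. It is probably favourable to the programme to the extent that people leave because of burden.

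Each leaver removes one sixth of the planned ratings. Under the assumed 10% to 30% withdrawal, the chance of losing at least one is 47% to 88%. These figures rest on assumed rates and on independence between participants, and they say nothing about how low a leaver's rating would be. The primary swallowing outcomes are not affected. The change is worth making before recruitment, because the missing ratings cannot be reconstructed later.

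**What to change.** 1. In the unnumbered assessment schedule of section 6.2 (not Table 1, which is the study timeline) and in the Probes text, add that the questionnaire is offered, with consent, at exit. It should go to any participant who has had at least one therapy session and leaves before the post-treatment assessment, whether by own choice or by researcher decision.
2. In section 6.7, add an exception to the rule that data collection stops at withdrawal, limited to this questionnaire and subject to the participant's consent.
3. In section 6.7.1, extend the exit contact to researcher-initiated withdrawals, for which none is described.
4. State that acceptability is reported for everyone who started therapy, with completers and leavers shown separately, beside the number of withdrawals and their reasons. Say that these records contribute to Aim 1.

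The cost is a few minutes for a departing participant, who may decline, and a small amendment for ethics review. Some exit questionnaires will be refused or impossible to obtain, and those should be counted and reported as missing. Treatment, sample size and primary outcomes do not change.

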### **6.3 Population/ Calculation of sample size**

Sample size calculation: This is a phase 1 study to acquire data for a sample size calculation. Considering no protocol exists for ultrasound visual feedback in dysphagia rehabilitation in people with Parkinson's, the researchers will first aim to assess the feasibility of use with a single participant. Subsequently, n=6 will be recruited to allow for attrition expected in behavioural rehabilitation. This follows a similar sample size to other pilot studies (Blyth, McCabe, Madill, & Ballard, 2017).

### **6.4 Participant Enrolment and Randomisation**

#### *6.4.1 Recruitment*

Participants will be recruited as detailed in the procedure in page 9.

#### *6.4.2 Inclusion and Exclusion Criteria*

Inclusion Criteria: Participants with:

1. Confirmed diagnosis of Idiopathic Parkinson's Disease by a neurologist
2. Self-reported change in swallow function since diagnosis of Parkinson's Disease
3. Ability to assent to participation in study (either verbal or written)
4. Presence of oral phase dysphagia as assessed by a speech pathologist.
5. Medically stable and living in the community.

Exclusion Criteria: Participants who are/have:

1. Other concomitant neurological disorders
2. A history of head and neck cancer
3. Unmanaged hearing or vision difficulties
4. Nil by Mouth status.
5. Unable to communicate in English
6. Hospitalised with a respiratory tract infection in the last 12 weeks.

#### *6.4.3 Randomisation and Blinding Processes*

As it is a behavioural study, participants and the therapist will not be blinded to the intervention. However, the assessors will be blinded to the sequence in which the probe data is collected (i.e., the assessor will review the task recordings to obtain the probe data and will not know which week a specific recording was obtained). This will be achieved by getting an independent person to re-order the recordings of sessions so that they are not chronological, and the assessors will evaluate the outcome measures without knowing if they are from the baseline or intervention phase. Participants will be randomised into different lengths and onset of baseline phase prior to assessment.

### **6.5 Primary and Secondary Outcome Measures**

The primary outcome measures include:

- Timed Water Swallow Test (TWST) (Hughes & Wiles, 1996; Sarve et al., 2021)

- Test of Masticating and Swallowing Solids (TOMASS) (Athukorala et al., 2014; Huckabee et al., 2018)

Secondary outcome measures:

- Texture of food as per the International Dysphagia Diet Standardisation Initiative Level (IDDSI) (Cichero et al., 2017)
- Consistency of liquid as per the the International Dysphagia Diet Standardisation Initiative Level (IDDSI) (Cichero et al., 2017)
- Observational measures rated with an ultrasound probe under the chin.
  - Changes in components 2, 3, 4 and 5 listed on the Modified Barium Swallow Impairment Profile (MBSImp) (Martin-Harris et al., 2008) which is a rating scale that rates key physiological aspects of swallowing in the different phases. Components 2, 3, 4, and 5 are specifically related to the oral phase of swallowing.
  - Average time taken to swallow a single sip of liquid (ml/s)
  - Time taken to swallow (a) ½ biscuit (b) a dessert spoon of diced fruit and (c) a dessert spoon of puree
  - Number of times the participant needs to swallow to clear a single, controlled sip of liquid (number of swallows/ml)
  - Number of times the participant needs to swallow to clear (a) ½ biscuit (b) a dessert spoon of diced fruit and (c) a dessert spoon of puree from their mouth
- Patient reported measures:
  - Time taken to complete meals
  - Swallowing Quality of Life Questionnaire (SWAL-QoL) (McHorney et al., 2002)
  - Theoretical Framework of Acceptability based questionnaire (Sekhon, Cartwright & Francis, 2022)
  - Swallowing Disturbance Questionnaire - PD (SDQ-PD)

Control measures

- Maximum Phonation Time (Speyer et al., 2010)
- Speech Rate (Syllables per minute during a 30 second monologue)
- Average decibels in 30 second monologue
- Intelligibility Rating of monologue using the Frenchay-2 Rating scale (perceptual) (Enderby & Palmer, 2008)

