OUTCOMES	
The primary outcome measures include:
 
 
• Timed Water Swallow Test (TWST) (Hughes & Wiles, 1996; Sarve et al., 2021)
 
• Test of Masticating and Swallowing Solids (TOMASS) (Athukorala et al., 2014; Huckabee et al., 2018)
 
 
Secondary outcome measures:
 
 
• Texture of food as per the International Dysphagia Diet Standardisation Initiative Level (IDDSI) (Cichero et al., 2017)
 
• Consistency of liquid as per the the International Dysphagia Diet Standardisation Initiative Level (IDDSI) (Cichero et al., 2017)
 
• Observational measures rated with an ultrasound probe under the chin. 
 
○ Changes in components 2, 3, 4 and 5 listed on the Modified Barium Swallow Impairment Profile (MBSImP) (Martin-Harris et al., 2008) which is a rating scale that rates key physiological aspects of swallowing in the different phases. Components 2, 3, 4, and 5 are specifically related to the oral phase of swallowing.
 
○ Average time taken to swallow a single sip of liquid (ml/s)
 
○ Time taken to swallow (a) ½ biscuit (b) a dessert spoon of diced fruit and (c) a dessert spoon of puree
 
○ Number of times the participant needs to swallow to clear a single, controlled sip of liquid (number of swallows/ml)
 
○ Number of times the participant needs to swallow to clear (a) ½ biscuit (b) a dessert spoon of diced fruit and (c) a dessert spoon of puree from their mouth
 
 
 
• Patient reported measures: 
 
○ Time taken to complete meals
 
○ Swallowing Quality of Life Questionnaire (SWAL-QoL) (McHorney et al., 2002)
 
○ Theoretical Framework of Acceptability based questionnaire (Sekhon, Cartwright & Francis, 2022)
 
 
 
 
Control measures
 
 
• Maximum Phonation Time (Speyer et al., 2010)
 
• Speech Rate (Syllables per minute during a 30 second monologue)
 
• Average decibels in 30 second monologue
 
• Intelligibility Rating of monologue using the Frenchay-2 Rating scale (perceptual) (Enderby & Palmer, 2008)
 

STUDY DURATION	Estimated study duration from initial enrolment until completion of data analyses is 24 months.
INTERVENTION/S	Behavioural dysphagia rehabilitation with ultrasound biofeedback

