### **Screener:**

As part of the screening process, participants will answer questions pertaining to the inclusion and exclusion criteria to determine their eligibility for the study. This process should take ~30 minutes and will be completed over the phone. If potentially eligible for the study, potential participants will be invited to enrol in the study and undergo the next steps in the informed consent process.

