## Assessment

Following screening and consent, participants will be assessed by a qualified speech pathologist (one of the investigators) using standard speech pathology tools. As shown on page 8, the assessment will include the (a) Timed Water Swallow Test (TWST) (Hughes & Wiles, 1996; Sarve et al., 2021), (b) Test of Masticating and Swallowing Solids (TOMASS) (Athukorala et al., 2014; Huckabee et al., 2018), (c) a clinical swallow trial with the ultrasound to determine severity of oral phase deficits based on a checklist based on components 2, 3, 4 and 5 of the Modified Barium Swallow Impairment Profile (MBSImp) (Martin-Harris et al., 2008) (d) questions about the type of modification they need for the meal based on the The International Dysphagia Diet Standardisation Initiative Level (IDDSI) (Cichero et al., 2017), (e) the time taken to complete meals, and the (f) Swallowing Quality of Life Questionnaire (SWAL-QoL) (McHorney et al., 2002).

Control measures including the (a) Maximum Phonation Time, (b) Speech Rate (Syllables per minute during a 30 second monologue), (c) Average decibel in 30 second monologue and (d) Percent Intelligibility Rating based on Frenchay-2 Rating scale (perceptual) (Enderby & Palmer, 2008) will be recorded.

The assessment will be audio and video recorded. If participants experience fatigue, the assessments will be conducted over 2 sessions.

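### SDQ-PD is a secondary outcome in section 6.5 but is absent from the synopsis, and its only pre-treatment value is the telephone eligibility screener, so its pre-post change may be biased in an uncertain direction

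*Protocol*

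**What the plan says.** Section 6.5 of the protocol names "Swallowing Disturbance Questionnaire - PD (SDQ-PD" as the last of its patient-reported secondary outcomes. The synopsis has the same patient-reported group, but its list stops at the "Theoretical Framework of Acceptability based questionnaire" and has no SDQ-PD.

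The schedule in section 6.2 has a row for "Swallowing Disturbance Questionnaire (SDQ-PD) (Manor et al., 2007) (Questionnaire". It carries a mark under Screener and two later marks. There is none under Assessment, the A1 baseline or the treatment phase.

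The Screener text in section 6.2 says that "participants will answer questions pertaining to the inclusion and exclusion criteria to determine their eligibility for the study", and adds: "This process should take ~30 minutes and will be completed over the phone". Enrolment and the main consent process follow.

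The Assessment text lists swallowing items (a) to (f), ending with "f) Swallowing Quality of Life Questionnaire (SWAL-QoL) (McHorney et al., 2002". SDQ-PD is not among them. The Probes text says that after the treatment phase "a repeat assessment will be completed (identical to the one conducted at the start of the treatment program) by a qualified speech pathologist", and then adds the acceptability questionnaire.

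**The concern.** A questionnaire used as an outcome needs a pre-treatment value obtained under the same conditions as the later values. For SDQ-PD the only earlier value comes from the call in which the person's eligibility is being decided. Later values come from the post-treatment assessment and the four-week follow-up. Setting, stage of the study and possibly mode of administration therefore change at the same time as treatment status.

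The rest of the design does not protect this measure. The probe measures have 6 or 9 baseline values per participant and staggered baselines; SDQ-PD has a single earlier score. There is no concurrent control group, participants know they are treated, and the score is self-reported. Any shift due to the changed circumstances would be mixed with the treatment effect.

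The omission from the synopsis is a separate, smaller matter: the two outcome lists disagree on whether SDQ-PD is a secondary outcome at all.

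**Working it through.** The protocol gives no SDQ-PD figure, so there is nothing to reproduce. The check is a comparison of texts, a calculation of elapsed time, and a test of whether a size of bias can be derived.

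**1. Where each questionnaire is scheduled (section 6.2 table)**

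| Measure | Screener | Assessment | A1 and treatment probes | Post-treatment assessment | Four-week follow-up |
|---|---|---|---|---|---|
| SDQ-PD | yes | no | no | yes | yes |
| SWAL-QoL | no | yes | no | yes | yes |
| Acceptability questionnaire | no | no | no | yes | no |

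The table is split in the available text, and its second part has one column more than its header. The SDQ-PD mark in the first position and the blanks under Assessment, A1 and treatment are clear. The two later positions are inferred: they coincide with the later SWAL-QoL marks, and the first coincides with the only mark for the acceptability questionnaire, which the Probes text places after treatment.

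**2. Elapsed time**

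Inputs: baseline of 2 or 3 weeks (Probes), a four-week intervention (section 4.2), and follow-up four weeks after therapy ends (schedule).

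- Screener to end of treatment: at least 2 + 4 = 6 or 3 + 4 = 7 weeks.
- Screener to follow-up: at least 6 + 4 = 10 or 7 + 4 = 11 weeks.

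The unstated gap between the screener and the start of baseline comes on top. The pre-treatment assessment also precedes baseline, so SWAL-QoL spans most of the same interval. What sets SDQ-PD apart is the eligibility stage, the telephone setting and that extra gap.

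**3. Can a size of bias be derived?**

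If entry required a score above a cut-off, regression to the mean in SD units would be (1 − ρ) × φ(c) / q. Here ρ is the test-retest correlation, q the share of people passing, c the standard normal cut-off for that share, and φ the normal density. The inclusion and exclusion criteria in the synopsis and in section 6.4.2 contain no SDQ-PD score or cut-off. With no selection on the score, q = 1 and the selection term is 0 SD at any ρ. A positive figure would need an invented cut-off, and the protocol gives no ρ either.

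A zero from this formula does not prove absence of bias. The same call asks for a self-reported change in swallowing (inclusion criterion 2), so a related self-report could select indirectly, and people may volunteer when symptoms are worse. In the other direction, section 7.2.1 warns of possible decline through disease progression. The effect of telephone versus later administration has no direction stated in the protocol, which also does not say how the later questionnaires are given.

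**The case against.** The strongest defence is that SDQ-PD is one of several secondary measures in a pilot of six people. The hypothesis concerns time taken to swallow, the primary outcomes are TWST and TOMASS, and SWAL-QoL already supplies a patient-reported measure with an assessment-stage baseline. The d2 and PND methods in section 6.14 compare repeated phase data, and no SDQ-PD pre-post test is stated. All of this stands, and it limits the weight of the point. It does not give SDQ-PD a comparable baseline.

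A reader might infer three stronger things that the protocol does not support:

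- **That the SDQ-PD change is biased towards improvement.** No criterion selects on the score. Criterion 2 asks whether swallowing has changed, not how severe it is on the day. Oral phase dysphagia is judged by a speech pathologist, and progression acts the other way. Indirect selection is possible but neither shown nor measurable.
- **That SDQ-PD would not be collected after treatment, because the repeat assessment is called identical and the Assessment text omits SDQ-PD.** That text refers to the schedule and is not exhaustive: the schedule marks a reading passage, a picture description and a rapid alternating sounds task at Assessment, and the text names none of them. Section 6.5 and the schedule agree that SDQ-PD is collected. At most, the word identical is loose.
- **That the screener score is taken without consent.** The Expression of Interest text provides a separate consent form for the screener.

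**Conclusion.** The point holds in limited form. SDQ-PD is a secondary outcome in section 6.5 but missing from the synopsis. Its single pre-treatment value is an eligibility-stage telephone score taken at least 6 to 7 weeks before treatment ends. The pre-post change may be biased in either direction, and no size can be given.

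This rests on two readings: that the schedule's Screener mark means the questionnaire is given in the screening call, and that the two later marks fall at the post-treatment assessment and the follow-up. Severity is minor, since the primary outcomes and the other secondary measures are unaffected. It is still worth correcting, because a missing pre-treatment value cannot be recovered later.

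**What to change.** - Mark SDQ-PD in the Assessment column of the section 6.2 schedule and add it to the Assessment text, given in the same way as at the post-treatment visit.
- In section 6.5, name that value as the SDQ-PD baseline, and keep the screener score for screening only.
- Add SDQ-PD to the patient-reported outcomes in the synopsis.
- In the Probes text, replace the claim that the two assessments are identical with wording that matches the schedule.

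This removes the difference in stage and setting, whichever way it acts, and the gap between screener and assessment. It does not shorten the baseline and treatment weeks, which SWAL-QoL also spans. The cost is a few minutes of participant time for one short questionnaire at an existing visit, plus the wording changes. It has to be in place before a participant's pre-treatment assessment.
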